## 4.2. Exclusion Criteria

Any potential subject who meets any of the following criteria will be excluded from participating in the study:

1. Involvement of the central nervous system by WM.
2. Evidence of disease transformation.
3. Prior exposure to ibrutinib or other BTK inhibitors.
4. Known hypersensitivity reaction (eg. Anaphylactic and anaphylactoid reactions) to ibrutinib or to the excipients in its formulation. Refer to the IB for a list of excipients.
5. Received any WM-related therapy (eg, chemotherapy, immunotherapy, investigational drug)  $\leq 30$  days prior to first administration of study treatment.
6. Received a prior allogeneic hematopoietic stem cell transplant.
7. Plasmapheresis  $< 35$  days prior to the initiation of study drug, except when at least one serum IgM central assessment was performed during the screening period and was  $> 35$  days from the most recent plasmapheresis procedure.
  - Subjects with high IgM values or viscosity symptoms during screening may receive plasmapheresis prior to initiating study drug (refer to Section 8.5) if the previous plasmapheresis was performed  $> 35$  days before the plasmapheresis performed during screening (in order to obtain a true baseline IgM value for efficacy evaluations).
8. History of other malignancies, except:
  - Malignancy treated with curative intent and with no known active disease present for  $\geq 2$  years before the first dose of study drug and felt to be at low risk for recurrence by treating physician.
  - Adequately treated non-melanoma skin cancer or lentigo maligna without evidence of disease.
  - Adequately treated carcinoma in situ without evidence of disease.
9. Vaccinated with live, attenuated vaccines within 4 weeks of first dose of study drug.
10. Infection requiring systemic treatment that was completed  $\leq 14$  days before the first dose of study drug.
11. Bleeding disorders (eg, von Willebrand's disease) or hemophilia.
12. Stroke or intracranial hemorrhage within 6 months prior to enrollment.

13. Infection with human immunodeficiency virus (HIV).
14. Active infection with hepatitis B or hepatitis C.
  - Note: If Hepatitis B surface antigen (HBsAg) is positive, the subject is excluded. Hepatitis B DNA polymerase chain reaction (PCR) needs to be confirmed negative prior to first study agent administration in subjects who are Hepatitis B core antibody positive. If Hepatitis C antibody is positive, RNA PCR needs to be performed and confirmed negative prior to the first study agent administration. Patient with history of Hepatitis C virus infection should have documented 24wks of sustained virologic response (SVR) in order to be eligible for the study.
15. Major surgery (as defined in Section [8.4.2](#)) within 4 weeks of first dose of study drug.
16. Any life-threatening illness, medical condition, or organ system dysfunction that, in the investigator's opinion, could compromise the subject's safety or put the study outcomes at undue risk.
17. Currently active, clinically significant hepatic impairment Child-Pugh Class B or C according to the Child Pugh classification (see [Attachment 4](#)).
18. Currently active, clinically significant cardiovascular disease, such as uncontrolled arrhythmia or Class 3 or 4 congestive heart failure as defined by the New York Heart Association Functional Classification ([Attachment 7](#)); or a history of myocardial infarction, unstable angina, or acute coronary syndrome within 6 months prior to first dose.
19. Requires or receiving anticoagulation with warfarin or other Vitamin K antagonists (eg, phenprocoumon).
20. Unable to swallow capsules or malabsorption syndrome, disease significantly affecting gastrointestinal function, or resection of the stomach or small bowel, symptomatic inflammatory bowel disease or ulcerative colitis, or partial or complete bowel obstruction.
21. Requires treatment with a strong cytochrome P450 (CYP) 3A inhibitor (see [Attachment 3](#)).
22. Lactating or pregnant.
23. Unable to understand the purpose and risks of the study and to provide a signed and dated informed consent form (ICF) and authorization to use protected health information (in accordance with national and local subject privacy regulations).

**NOTE:** Investigators should ensure that all study enrollment criteria have been met at screening. If a subject's clinical status changes (including any available laboratory results or receipt of additional medical records) after screening but before the first dose of study drug is given such that he or she no longer meets all eligibility criteria, then the subject should be excluded from participation in the study. Section 17.4, Source Documentation, describes the required documentation to support meeting the enrollment criteria. Subjects who fail to meet the inclusion and exclusion criteria (ie, screen failures) may be rescreened once if their condition changes. Rescreening must be discussed with and approved by the sponsor on a case-by-case basis. Subjects who are determined to be eligible for rescreening must sign a new ICF and then will be assigned a new Screening number.

#### **4.3. Prohibitions and Restrictions**

Potential subjects must be willing and able to adhere to the following prohibitions and restrictions during the course of the study to be eligible for participation:

1. Refer to Section 8 for details regarding prohibited and restricted therapy during the study.
2. Agree to follow all requirements that must be met during the study as noted in the Inclusion and Exclusion Criteria (eg, contraceptive requirements).

The following guidance should be applied during the perioperative period for subjects who require surgical intervention or an invasive procedure while receiving study medication:

- For any surgery or invasive procedure requiring sutures or staples for closure, study medication should be held at least 7 days prior to the intervention and should be held at least 7 days after the procedure, and restarted at the discretion of the investigator when the surgical site is reasonably healed without serosanguineous drainage or the need for drainage tubes.
- For minor procedures (such as a central line placement, needle biopsy, thoracentesis, or paracentesis), study medication should be held for at least 3 days prior to the procedure and should not be restarted for at least 3 days after the procedure. For bone marrow biopsies that are performed while the subject is on study medication, it is not necessary to hold study medication for these procedures.
- For emergency procedures, study medication should be held after the procedure until the surgical site is reasonably healed, for at least 7 days after the urgent surgical procedure.

#### **5. TREATMENT ALLOCATION AND BLINDING**

Randomization will not be used in this study. Subjects will be enrolled to receive study treatment after eligibility is confirmed. As this is an open study, blinding procedures are not applicable.

#### **6. DOSAGE AND ADMINISTRATION**

Ibrutinib will be administered orally, once daily, at a dose of 420 mg (140 mg × 3 capsules taken together at one time). Protocol-specified dose modifications of ibrutinib will be made as

necessary. Study drug (3 capsules) is administered orally once daily with approximately 8 ounces (240 mL) of water. The capsules should be swallowed whole and should not be opened, broken, or chewed. The use of strong CYP3A inhibitors/inducers, and grapefruit and Seville oranges should be avoided for the duration of the study (Section 8.2 and Attachment 3).

If a dose is not taken at the scheduled time, it can be taken as soon as possible on the same day with a return to the normal schedule the following day. The subject should not take extra capsules to make up the missed dose. Missed doses of study drug will not be made up.

The first dose will be administered in the clinic on Day 1 of Week 1, after which study drug will be self-administered daily by the subjects on an outpatient basis. Study drug will be dispensed to subjects in bottles. Unused study drug dispensed during previous visits must be returned to the site and drug accountability records (Section 14.5) updated at each visit. Returned capsules must not be re-dispensed to anyone.

Study drug dosing is continuous (without interruptions) throughout the Treatment Phase.

## **6.1. Formulation/Packaging/Storage**

Ibrutinib capsules are provided as a hard gelatin capsule containing 140 mg of ibrutinib. All formulation excipients are compendial and are commonly used in oral formulations. Refer to the ibrutinib IB for a list of excipients.

The ibrutinib capsules will be packaged in opaque high-density polyethylene plastic bottles with labels bearing the appropriate label text as required by governing regulatory agencies. All study drugs will be dispensed in child-resistant packaging. Refer to the pharmacy manual/site investigational product manual for additional guidance on study drug storage, preparation and handling. Study drug labels will contain information to meet the applicable regulatory requirements.

## **6.2. Overdose**

Any dose of study drug administered in excess of that specified in this protocol is considered to be an overdose. Signs and symptoms of an overdose that meet any Serious Adverse Event criterion must be reported as a Serious Adverse Event in the appropriate time frame and documented as clinical sequelae to an overdose.

There is no specific experience in the management of ibrutinib overdose in patients. No maximum tolerated dose was reached in the Phase 1 study in which subjects received up to 12.5 mg/kg/day (1,400 mg/day). Healthy subjects were exposed up to single dose of 1,680 mg. One healthy subject experienced reversible Grade 4 hepatic enzyme increases (AST and ALT) after a dose of 1,680 mg. Subjects who ingested more than the recommended dosage should be closely monitored and given appropriate supportive treatment. Refer to Section 12 for further information regarding AE reporting (refer to Section 12.3.2 for Special Reporting Situations).

### **6.3. Dose Hold, Reduction or Discontinuation of Study Drug**

Treatment with study drug should be withheld for any unmanageable, potentially study drug-related non-hematological toxicity that is Grade 3 or higher in severity and any hematologic toxicity meeting the criteria in Section 6.4. Subjects who require full-dose of anticoagulant treatment (eg, heparin) should have study drug held until stable on anticoagulant therapy (Section 8.2.3). Subjects that require an invasive procedure or surgery must have study drug withheld according to the guidance in Section 6.2. Any other clinically important events where dose delays may be considered appropriate by the Investigator must be discussed with the Medical Monitor.

Study drug may be withheld for a maximum of 28 consecutive days for toxicity. Study drug should be discontinued in the event of a toxicity lasting more than 28 days, unless reviewed and approved by the Medical Monitor.

### **6.4. Dose Modification of Study Drug**

The dose of study drug should be modified according to the dose modification guidance in Table 2 if any of the following drug-related toxicities occur:

- Grade 3 or greater neutropenia with infection or fever
- Grade 4 ANC (<500/ $\mu$ L) for more than 7 days. The use of neutrophil growth factors is permitted per American Society of Clinical Oncology (ASCO) guidelines and must be recorded in the electronic case report form (eCRF). Refer to Section 8 for instruction regarding the use of growth factor support.
- Grade 3 thrombocytopenia (platelets <50,000/ $\mu$ L) in the presence of Grade  $\geq 2$  bleeding events.
- Grade 4 thrombocytopenia (platelets <25,000/ $\mu$ L).
- Grade 3 or 4 nausea, vomiting, or diarrhea if persistent, despite optimal anti-emetic and/or anti-diarrheal therapy.
- Any other Grade 4 or unmanageable Grade 3 toxicity attributed to study drug.

For Grade 3 or 4 atrial fibrillation or persistent atrial fibrillation of any grade, consider the risks and benefits of ibrutinib treatment. If clinically indicated, the use of anticoagulants or antiplatelet agents may be considered for the thromboprophylaxis of atrial fibrillation (Section 8.2.3).

**Table 2: Study Drug Dose Modifications**

Occurrence	Action
First	Withhold study drug until recovery to Grade $\leq 1$ or baseline; may restart at original dose level
Second	Withhold study drug until recovery to Grade $\leq 1$ or baseline; may restart at 1 dose level lower (ie, 280 mg/day/2 capsules)
Third	Withhold study drug until recovery to Grade $\leq 1$ or baseline; may restart at 1 dose level lower (ie, 140 mg/day/1 capsule)
Fourth	Discontinue ibrutinib a

a. If the oral study drug is discontinued for toxicity, subject will end the Treatment Phase of the study.

Please see Section [8.2.1](#) for guidelines for management of study drug in subjects who require treatment with a strong CYP3A inhibitor.

Once there has been a dose reduction of ibrutinib, there will be no dose re-escalations. No dose escalation of ibrutinib (above 420 mg) is allowed in this study.

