## **6.5. Dose Modification for Hepatic Impaired Subjects**

Ibrutinib is metabolized in the liver. For subjects with mild liver impairment (Child-Pugh class A), the recommended dose for ibrutinib is 140 mg daily (one capsule). Subjects with moderate or severe hepatic impairment (Child-Pugh class B or C) should avoid using ibrutinib. Monitor subjects for signs of toxicity and follow dose modification guidance as needed.

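### Table 2's milligram figures fit only a 420 mg dose: for an eligible Child-Pugh A subject on 140 mg, the dose printed as one level lower is double the assigned dose

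*Protocol*

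**What the plan says.** Protocol Section 6.4 lists the qualifying drug-related toxicities and says: "The dose of study drug should be modified according to the dose modification guidance in Table 2". It makes no exception by starting dose.

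In Table 2, drug is withheld at each of the first three occurrences until recovery. After the first, the subject may resume the original dose. After the second, the subject "may restart at 1 dose level lower (ie, 280 mg/day/2 capsules". After the third, the subject "may restart at 1 dose level lower (ie, 140 mg/day/1 capsule". At the fourth, ibrutinib stops.

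Three notes follow the table. One points to Section 8.2.1 "for guidelines for management of study drug in subjects who require treatment with a strong CYP3A inhibitor". The others read: "Once there has been a dose reduction of ibrutinib, there will be no dose re-escalations" and "No dose escalation of ibrutinib (above 420 mg) is allowed in this study".

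Section 6.5 comes next. For mild liver impairment (Child-Pugh A), "the recommended dose for ibrutinib is 140 mg daily (one capsule". On toxicity in these subjects it adds only: "Monitor subjects for signs of toxicity and follow dose modification guidance as needed".

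**The concern.** Table 2 is written as a ladder down from 420 mg, but nothing in it says so, and the protocol puts some subjects on less than 420 mg from the outset or while they take another drug. A site with a Child-Pugh A subject on 140 mg who has a second qualifying toxicity is told to go one level lower and is given a figure that is higher. The third-occurrence row names the dose that the subject already takes.

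At stake is the handling of repeated serious toxicity in subjects whose dose was cut to one third because the drug is cleared by the liver. A clinician will probably see that 280 mg is wrong, but that does not show what is right. One site might restart at 140 mg and another might stop treatment, and each could claim to have followed the protocol. SAP Section 4.4 counts incorrect dosing as a category of major deviation, so the correct dose needs to be identifiable.

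**Working it through.** **Is the case reachable?** Exclusion criterion 17 (Protocol Section 4.2) bars only Child-Pugh B and C. Take a subject with mild liver impairment, albumin of 28 to 35 g/L, and every other item in Attachment 4 at one point. The score is bilirubin 1 + albumin 2 + INR 1 + ascites 1 + encephalopathy 1 = 6, and class A is 5 to 6. Albumin is not among the laboratory entry limits in Section 4.1. Such a subject can enrol and is given 140 mg.

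**The plan's own ladder.** The only capsule is 140 mg (Section 6.1), and it may not be divided (Section 6). From the standard dose, 3 × 140 = 420, 2 × 140 = 280 and 1 × 140 = 140 mg. Table 2's figures are reproduced, and the table is coherent for that start.

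**The same rows applied to each assigned dose.** The ratio is the printed restart dose divided by the assigned dose.

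| Assigned dose | Second occurrence (280 mg) | Third occurrence (140 mg) | Whole-capsule levels below |
|---|---|---|---|
| 420 mg (3 capsules) | 280/420 = 0.67 | 140/420 = 0.33 | 3 − 1 = 2 |
| 280 mg (2 capsules; moderate CYP3A inhibitor) | 280/280 = 1.00 | 140/280 = 0.50 | 2 − 1 = 1 |
| 140 mg (1 capsule; Child-Pugh A) | 280/140 = 2.00 | 140/140 = 1.00 | 1 − 1 = 0 |

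The ratios describe the printed instruction. They are not a measure of risk or frequency.

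**Does other text resolve the Child-Pugh A case?**
- The re-escalation ban starts only after a dose reduction. A subject who began at 140 mg has arguably had none.
- The escalation ban is limited to doses above 420 mg.
- The overdose clause (Section 6.2) concerns doses beyond those that the protocol specifies, and 280 mg is itself printed in Table 2.
- The cross-reference under Table 2 leads to Section 8.2.1, not to Section 6.5.

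**CYP3A inhibitors.** Section 8.2.1 tells the site to reduce ibrutinib to 140 mg with voriconazole or low-dose posaconazole. That is a dose reduction in plain words, so the re-escalation ban rules out 280 mg while the inhibitor is in use. What is missing is a step below 140 mg, and neither Section 8.2.1 nor Attachment 5 supplies one. With a moderate inhibitor the dose is 280 mg, and the second-occurrence row then repeats the current dose.

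**How many subjects?** The documents give no rates. Assume for illustration that 5% to 10% of subjects are class A and that 10% to 20% of those have two qualifying toxicities. The expected number among 17 is 17 × 0.05 × 0.10 = 0.09 to 17 × 0.10 × 0.20 = 0.34.

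**The case against.** The strongest reply is that no competent reader would double the dose. The table says lower, and restart is permitted, not required. Drug is withheld until recovery. Section 6.3 ends treatment for toxicity beyond 28 days unless the Medical Monitor approves otherwise. Section 10.2 allows discontinuation for unacceptable toxicity or in the subject's interest. Section 17.1 tells the investigator to contact the sponsor, normally beforehand, when a departure from the protocol cannot be avoided. Section 6.5 is also the specific rule for these subjects and is headed as a dose modification. Its 140 mg could therefore be read as a reduction from 420 mg, and the re-escalation ban would then apply.

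Most of this stands, and it settles the size of the point. It does not remove it. The reading of Section 6.5 as a reduction is arguable, because that section calls 140 mg the recommended dose and speaks of no reduction. Even on that reading, the subject has no valid step at the second or third occurrence. The 28-day rule does not reach a subject who recovers sooner. Contacting the sponsor about a departure is a fallback where the written rule fails.

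A reader might infer that subjects on voriconazole or low-dose posaconazole face the same printed doubling. The documents do not support that: the re-escalation ban covers these subjects, and only the missing lower step remains. Exclusion criterion 21 also keeps out subjects who need a strong inhibitor at entry.

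**Conclusion.** The point holds as a minor dosing-safety correction. Table 2 is right for the trial's standard 420 mg dose and wrong as written for a small eligible subgroup. For Child-Pugh A subjects on 140 mg, the second-occurrence figure is twice the assigned dose, the third is no reduction, and no lower dose can be made from whole capsules. Subjects on 280 mg with a moderate inhibitor get no reduction at the second occurrence.

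This rests on reading Section 6.4 as applying Table 2 to every treated subject, as its wording does, and on Section 6.5 being followed. The number affected is unknown and probably below one subject; the illustrative range of 0.09 to 0.34 depends wholly on assumed rates.

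Two stronger conclusions should not be drawn. The protocol does not require a doubled dose, and one is unlikely in practice; the realistic risk is inconsistent handling between sites. Nor does the point bear on the ORR analysis, whose population, threshold and interval do not depend on Table 2.

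**What to change.** Add this footnote to Table 2 and cite it in Section 6.5 and Attachment 5:

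> The milligram figures apply to subjects receiving 420 mg. For subjects on a lower dose because of hepatic impairment or a CYP3A inhibitor, one dose level lower means one capsule (140 mg) less than the dose at onset of the toxicity, and no restart dose may exceed the dose at onset (for CYP3A inhibitors, while the inhibitor is in use). At 140 mg no lower level exists; at a second or third occurrence, restart at 140 mg after recovery or discontinue, as agreed with the Medical Monitor.

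Defining the level by capsule count also covers subjects on 280 mg, who would be left without figures by a footnote written for 140 mg alone. The cost is one footnote, two cross-references and an occasional Medical Monitor consultation, a role that Section 6.3 already uses. Eligibility, sample size and analysis stay as they are.

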## **6.5. Dose Modification for Hepatic Impaired Subjects**

Ibrutinib is metabolized in the liver. For subjects with mild liver impairment (Child-Pugh class A), the recommended dose for ibrutinib is 140 mg daily (one capsule). Subjects with moderate or severe hepatic impairment (Child-Pugh class B or C) should avoid using ibrutinib. Monitor subjects for signs of toxicity and follow dose modification guidance as needed.

## **7. TREATMENT COMPLIANCE**

The investigator or designated study personnel will maintain a log of all study drug dispensed and returned. Drug supplies for each subject will be inventoried and accounted for throughout the study.

The study drug is to be prescribed only by the principal investigator or a qualified physician listed as a sub-investigator. Records should be kept on the study drug accountability form provided by the sponsor or its designee (any alternative forms must be preapproved by the sponsor). Administration of the study drug must be recorded in the subject's source documentation. The study drug may not be used for any purpose other than that outlined in this protocol, including other human studies, animal investigations, or in vitro testing.

## **8. PRESTUDY AND CONCOMITANT THERAPY**

All prestudy antineoplastic therapies, including those since diagnosis of WM, must be recorded at screening. Concomitant therapies will include only clinically significant prescription therapies, "significant" will be any medications which the investigator thinks important and are prescribed for AE. They must be recorded throughout the study beginning with the time of written informed consent to 30 days after the last dose of study drug. All concomitant therapies (prescription, nonprescription, herbal) being taken at the time of an SAE will be collected. The use of these medications/transfusions must be recorded in the eCRF.

All other therapies (over-the-counter medications except fish oil, vitamin E preparations; non-pharmacologic therapies such as electrical stimulation, acupuncture, special diets, exercise regimens) are not required to be recorded in the eCRF.

## **8.1. Permitted Concomitant Medications**

Supportive medications in accordance with standard practice (such as for emesis, diarrhea, etc.) are permitted. Use of granulocyte colony-stimulating factors or erythropoietin growth factors is permitted per institutional policy and in accordance with the ASCO guidelines (Smith 2006). Transfusions may be given in accordance with institutional policy.

Short courses ( $\leq 14$  days) of steroid treatment for non-WM related medical reasons (eg, joint inflammation, asthma exacerbation, rash, antiemetic use and infusion reactions) at doses that do not exceed 100 mg per day of prednisone or equivalent are permitted. In addition, for subjects with chronic medical conditions, continuous administration of up to 20 mg per day of prednisone or equivalent is permitted for the treatment of this medical condition where no acceptable therapeutic alternative is available.

